1. INTRODUCTION

This document describes the rules and conventions to be used in the presentation and analysis of efficacy, safety and biomarker data for the gantenerumab open label portion of the Protocol DIAN-TU-001. It describes the data to be summarized and analyzed, including specifics of the statistical analyses to be performed.

This statistical analysis plan (SAP) is based on protocol amendment 12, dated November 10, 2021.

Details of the analyses presented for the Data Safety Monitoring Board (DSMB) meetings are presented in a separate DSMB SAP.

2. STUDY OBJECTIVES

2.1. PRIMARY OBJECTIVE

The primary objective for the final analysis of the Open Label Extension (OLE) is to determine if continued treatment with gantenerumab at its target dose can result in continued or complete removal of brain amyloid plaque using cerebral amyloid imaging using [¹¹C]-Pittsburgh Compound B (PiB) amyloid PET imaging tracer ([¹¹C]PiB) Positron emission tomography (PET).

2.4. SAFETY OBJECTIVES

This study will assess safety and tolerability of SC gantenerumab up to 1500 mg Q2W in individuals at risk for DIAD. Safety endpoints used will be the incidence and severity of treatment-emergent adverse events (TEAEs), serious adverse events (SAEs) and treatment discontinuations. Analysis will be on an intent-to-treat basis. Clinical laboratory evaluations, vital signs, and 12-lead ECGs will also be measured throughout the study. Amyloid-related imaging abnormalities (ARIA) are a safety endpoint in this study.

3. STUDY DESIGN

3.1. GENERAL DESCRIPTION

This SAP refers to the open label period of the trial following a Phase II/III double-blind, placebo-controlled study of potential disease modifying therapies in individuals with or at risk for dominantly inherited Alzheimer's disease (AD).

1. **What is the primary purpose of the study?** The study aims to evaluate the effectiveness of a new treatment for hypertension in a diverse population.

2. **What are the key variables being measured?** The primary outcome is blood pressure reduction, measured at baseline, 3 months, and 6 months. Secondary outcomes include changes in heart rate, blood glucose levels, and lipid profiles.

3. **What is the study design?** The study is a randomized controlled trial (RCT) comparing the new treatment (Group A) against a standard treatment (Group B). Both groups will receive the same diet and exercise interventions.

4. **Who is eligible to participate?** Adults aged 18-65 with a systolic blood pressure of 140 mmHg or higher, who are not currently on hypertension medication, are eligible. Exclusion criteria include pregnancy, history of stroke, and certain cardiovascular diseases.

5. **What is the timeline for the study?** The study will last 12 months, with a 6-month follow-up period. Recruitment is expected to start in March 2024 and end in August 2024.

6. **What is the budget for the study?** The total budget is approximately \$500,000, which includes salaries for researchers, equipment costs, and participant compensation.

7. **What are the potential risks and benefits of the study?** The study is considered safe and has the potential to improve the lives of participants by providing them with a new treatment option for hypertension. The risks are minimal, including side effects from the treatment or study procedures.

8. **What are the plans for dissemination of results?** The results will be published in peer-reviewed journals and presented at professional conferences. The findings will also be communicated to healthcare providers and the general public through media outlets.

The double-blind period had two arms for each study drug, the active study drug and the blinded placebo for that study drug. Subjects were recruited from various sources, i.e., participating DIAN-observational (DIAN-OBS) study sites, DIAN-TU-001 trial sites, DIAN-TU-001 partner sites, the DIAN Expanded Registry study, and families identified by the sites. Mutation positive subjects who signed the informed consent form (ICF), met eligibility requirements and completed all baseline evaluations were randomized in a 3:1 ratio to receive either the active study drug or placebo for the active study drug. Eligible subjects were offered the opportunity to receive active drug for up to 3 years in an open label extension.

Mutation positive subjects who were administered either gantenerumab/placebo to gantenerumab or solanezumab/placebo to solanezumab were allowed to participate in the OLE for gantenerumab. All subjects participating in the OLE will receive gantenerumab. Dosing and titration for the OLE can be found in Section 1.5.2 of Appendix 3 of the protocol.

3.2. SCHEDULE OF EVENTS

Schedule of events for the OLE can be found in Appendix 3 of the protocol.

3.3. CHANGES TO ANALYSIS FROM PROTOCOL

Two additional mITT populations, the OLE Gant All Gant exposure mITT and All Gant exposure mITT, will be used as supportive analysis populations for selected efficacy parameters, noting that linear models for these populations containing double-blind data will allow for the use of two slopes, one for double-blind baseline to open-label baseline and the second for open-label baseline through Year 3 of the open-label period. Parameters for analysis are included in this SAP based on OLE primary, secondary and exploratory endpoints and do not reflect all of the parameters identified for the analysis of the double-blind period.

Document: \\quintiles.net\enterprise\apps\sasdata\SASb\SAS\Washington_University\DIAN\SZA59524\Biostatistic
s\Documentation\SAP\CSR\DIANTU001_GantOLE_CSR_SAP_v7_07Dec2023

Author: [REDACTED] Version Number: 7

Version Date: 07Dec2023

Template No.: CS_TP_BS016 Revision 6

Reference: CS_WI_BS005

Effective Date: 02Dec2019

4. PLANNED ANALYSES

The following analyses will be performed for the gantenerumab OLE for this study:

- Analyses for DSMB meetings
- Interim Analysis
- Final Analysis

4.1. DATA SAFETY MONITORING BOARD (DSMB)

A DSMB SAP, describing the methodology and the presentation of, and access to, results will be provided by [REDACTED] as a separate document.

4.2. FINAL ANALYSIS

All final, planned analyses identified in this SAP will be performed by [REDACTED] following Sponsor Authorization of this Statistical Analysis Plan, Database Lock, and Sponsor Authorization of Analysis Sets.

Results from selected post hoc exploratory analyses which are not identified in this SAP but are deemed relevant to support the planned trial analyses will be documented and reported in the clinical study report (CSR); these results will be clearly identified as post hoc.

Exploratory analyses not performed for the study CSR such as exploratory biomarker analysis or OLE Baseline comparisons will be described by the Sponsor in a separate document. Analysis of pharmacokinetic parameters will be assessed by [REDACTED] and will be described in a separate document.

[REDACTED] [REDACTED]

Author: [REDACTED]

Version Number: 7

Version Date: 07Dec2023

Template No.: CS_TP_BS016 Revision 6

Reference: CS_WI_BS005

Effective Date: 02Dec2019

4.3. INTERIM ANALYSIS

An interim analysis for selected clinical/cognitive and biomarker endpoints will be conducted based on a datacut with all visits conducted through 31 March 2023, at which time it is projected that there will be a sufficient number of subjects with data collected at the Year 2 visit. The objectives of the interim are to determine if gantenerumab high dose and/or long term treatment result in clinical benefit and to determine whether the high dose of gantenerumab results in substantially increased amyloid removal compared to the double-blind period.

All visits up to the last visit contributing to interim efficacy assessments, including unscheduled visits, will be frozen at the time of the interim. All populations planned for final analysis will also be created for the interim, with the exception that external controls identified from DIAN-OBS may differ due to a different datacut being used for the interim and final analysis. A set of subject listings supporting parameters used for the interim analysis from the open-label database will be produced. Tables to be produced for the interim will be identified throughout the SAP, with analyses of efficacy described in [Section 17](#) with references to the corresponding [Section 16](#) where applicable.

Analysis of pharmacokinetic parameters will be assessed by [REDACTED] and will be described in a separate document.

5. ANALYSIS SETS

Agreement and documentation of mutation positive subjects included/excluded from each analysis set will be conducted prior to database lock for the OLE. Treatment groups for all analysis sets will be represented as follows and in the given order, noting that “Double-Blind Treatment Arm” will be displayed above the individual treatment columns:

Author: [REDACTED]	Version Number:	7
	Version Date:	07Dec2023
Template No.: CS_TP_BS016 Revision 6	Reference:	CS_WI_BS005
Effective Date: 02Dec2019		

Copyright © 2009, 2010, 2012, 2016, 2018, 2019 [REDACTED] All rights reserved. The contents of this document are confidential and proprietary to [REDACTED] Holdings Inc. and its subsidiaries. Unauthorized use, disclosure or reproduction is strictly prohibited.

- Placebo
- Solanezumab
- Gantenerumab
- Total

A set of controls will be used for efficacy analysis. The control groups are identified in the figures within [Section 5.3](#) and are described within [Section 5.4](#).

5.1. PROCESS FOR ANALYSIS SET ASSIGNMENT

- Analysis sets will be assigned based on SAP definitions. Subjects excluded from each analysis set and reason for exclusion will be prepared for the blind data review meeting prior to interim datacut and prior to database lock.
- After the data review meeting, any changes agreed upon during the meeting will be incorporated and the analysis sets will be finalized and signed off on by the Sponsor prior to the associated data transfer.

5.2. ALL SUBJECTS ENROLLED SET [ENR]

The all subjects enrolled (ENR) set will contain all mutation positive subjects who provided informed consent for the gantenerumab OLE.

5.3. MODIFIED INTENT-TO-TREAT [mITT]

The mITT analysis populations include all enrolled mutation positive subjects who receive any treatment post-baseline and have at least one assessment for the analysis primary parameter (PiB-PET SUVR for final analysis, CDR Global for both the interim analysis and the final analysis) prior to the associated treatment period (as a baseline assessment) and a post-baseline assessment. For analysis of clinical/cognitive endpoints or non-PET biomarker endpoints, the mITT population identified based on CDR Global should be used.

Author: [REDACTED]

Version Number:

7

Version Date:

07Dec2023

[figure not shown]
Template No.: CS_TP_BS016 Revision 6

Reference: CS_WI_BS005

Effective Date: 02Dec2019

There will be three separate mITT populations:

1. OLE Gant mITT: Any subjects in the OLE meeting mITT criteria using OLE baseline (defined as the last assessment time for the analysis primary parameter prior to the first dose of OLE treatment) as the baseline reference point. Refer to figure below where the data contributing to the population is highlighted in yellow (and denoted with '(Tx)') for the OLE period, regardless of double-blind treatment, with controls (further described in [Section 5.4](#)) highlighted in green from both placebo double-blind only subjects and matched controls from DIAN-OBS.

2. OLE Gant All Gant exposure mITT: Any subjects treated with gantenerumab in both the DB and OLE who meet mITT criteria using DB baseline as the baseline reference point. Refer to figure below where the data contributing to the population is highlighted in yellow (and denoted with '(Tx)') for subjects treated with gantenerumab in both DB and

Author: [REDACTED]

Version Number:

7

Version Date:

[figure not shown]
07Dec2023

Template No.: CS_TP_BS016 Revision 6

Reference: CS_WI_BS005

Effective Date: 02Dec2019

OLE, with main set controls (further described in [Section 5.4](#)) highlighted in green from both placebo double-blind only subjects and matched controls from DIAN-OBS, and an additional set of extended controls (using DB and OLE baseline values for double-blind placebo subjects entering OLE) in a different shade of green to be added to the main set controls to form a second set of controls for the population.

3. All Gant exposure mITT: Any subjects treated with Gantenerumab in either DB or OLE who meet mITT criteria using the baseline associated with the first period of Gantenerumab exposure as the baseline reference point. Refer to figure below where the data contributing to the population is highlighted in yellow (and denoted with 'Tx') any period of planned gantenerumab treatment, regardless of double-blind treatment, with controls (further described in [Section 5.4](#)) highlighted in green from both placebo double-

Author: [REDACTED]

Version Number:

7

Version Date:

[figure not shown]
07Dec2023

Template No.: CS_TP_BS016 Revision 6

Reference: CS_WI_BS005

Effective Date: 02Dec2019

blind only subjects and matched controls from DIAN-OBS.

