In the DIAN-TU-001 study, there was no benefit of gantenerumab observed on the primary endpoint, the DIAN Multivariate Cognitive Endpoint (DIAN-MCE), or on clinical endpoints Clinical Dementia Rating Sum of Boxes (CDR-SB) and Functional Assessment Scale (FAS). However, potential cognitive impact was inconclusive given that the asymptomatic placebo group showed no cognitive decline, and symptomatic patients had declined substantially before reaching target doses. Gantenerumab significantly reduced brain A β deposition, cerebrospinal fluid (CSF) total tau, and CSF pT181, and attenuated the increase of neurofilament light chain

(NfL). A β Pittsburgh compound B positron emission tomography (PiB-PET) results demonstrated significant reduction of A β deposition with gantenerumab compared to placebo at years 2 and 4. Gantenerumab was safe and well tolerated in doses up to 1200 mg SC Q4W (G3). During the placebo-controlled period of the trial, amyloid-related imaging abnormalities-cerebral edema (ARIA-E) were observed in 19.2% (10/48) of the gantenerumab group; compared to the placebo group, participants in the gantenerumab arm were more likely to develop ARIA-E (odds ratio [OR]=9.29, 95% confidence interval [CI]=[1.1, 75.9], p<0.05). ARIA-E cases were PiB+ and 60% had cognitive impairment (CDR>0). ARIA-E cases were mostly asymptomatic for lesion associated neurologic change (8/10); if symptoms occurred (2/10), they were mild in nature and resolved. ARIA-E events were managed by temporarily withholding the dose and resuming at similar or lower doses, with most reaching the target dose (3/10 ARIA-E cases discontinued from the trial, mainly to AD progression). APOE genotype was predictor of ARIA-E. ARIA-E frequency was 31% in APOE- ϵ 4+ and 14% in APOE- ϵ 4- (OR=5.0, 95%; CI [1.0, 30.4], p=0.055). Seventy (70) percent of the ARIA-E cases occurred at higher doses (900 mg or more) and generally after 2 doses of a titration dose. However, the mean severity as measured by Barkhof score was similar regardless of the dose (higher dose=2.8 vs lower doses=3.5).

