3.2.1 OLE Visit 1 (baseline/first dose)

Location: DIAN-TU site.

Time/Timing: Approximately a 2 to 3 day visit that is scheduled after the decision is made to continue the drug arm in the OLE. If possible, the study partner should accompany the participant to the DIAN-TU site for this visit. For participants who live near the study site, these visit procedures may be scheduled over a longer time period of up to 2 weeks. If this is not possible, the study partner procedures can be completed via telephone. The sequence and timing of visit procedures is very important. Requirements and suggested timing of events are detailed in the *Global Manual of Operations*.

Note: The date during OLE Visit 1 when the first dose of study drug is administered should be used for determining timing of all subsequent visits.

Procedures:

- Obtain informed consent. Participants who wish to join the OLE may sign informed consent once a decision regarding OLE has been communicated by the sponsor and an approved OLE ICF is available at the site. This will enable ample time for review and consideration of the consent, and genetic counseling prior to dosing in the OLE.

- The following must be confirmed for the participant to be eligible for the OLE:
 - (i) participated in the double-blind period,
 - (ii) has a confirmed trial-eligible pathogenic DIAD variant,
 - (iii) in the opinion of the investigator and sponsor, treatment is not contraindicated for safety,
 - (iv) is capable of receiving drug and appropriate clinical safety assessments
- Vital signs (blood pressure, heart rate, respiratory rate, body temperature), weight and height
- Concomitant medication review
- Adverse event assessment
- Administration of C-SSRS
- 12-lead ECG; the ECG should be performed locally
- Blood collection for the following:
 - Clinical laboratory tests (hematology, chemistry, urinalysis)
 - Serum pregnancy test for people of childbearing potential (POCBP)
 - **CC1**
[REDACTED]; stored plasma and serum
- Physical and neurological examination
- Clinical assessments:
 - Clinical Dementia Rating (CDR) including calculation of Clinical Dementia Rating Sum of Boxes (CDR-SB)
 - Assessment of clinical diagnosis and clinician judgment of symptoms
 - **CC1**
[REDACTED]

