4.1.2 Biomarker Endpoint Power Analysis

Based on DIAN-TU-001 data from the double-blind period, the mean (SD) change from the OLE baseline in PiB-PET composite SUVR to the end of the 3-year OLE period with dosing up to CCI [REDACTED] CCI [REDACTED] is projected to be at least -0.473 (0.540) for participants on gantenerumab from the beginning of the double-blind period, and participants starting gantenerumab in OLE (having been on either active solanezumab or placebo) together. The recruitment goal of OLE is to enroll 60 to 90 of the 144 mutation positive participants who participated in the placebo-control period. Assuming an annual dropout rate of 5%, at the end of 3-year OLE, there will be 51 to 77 participants and it will provide over 99% power to detect the projected mean change from baseline using a one-sided one-sample t-test with type I error 0.025.

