5.4.2. INTERNAL SET CONTROLS

The internal set controls are defined as the placebo data from the double-blind period among subjects who did not enter the open-label extension.

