5.4.6. CONTROLS APPLIED TO INDIVIDUAL ANALYSIS POPULATIONS

Controls will be applied to the three mITT populations as follows, with the exception that Mixed Model for Repeated Measures (MMRM) analyses will be assessed against the internal set controls (when any controls are used) and parameters which are not assessed within DIAN-OBS will be assessed against the internal set controls:

- OLE Gant mITT: Evaluated against main set controls
- OLE Gant All Gant exposure mITT: Evaluated against main set controls (as primary set of controls) and also against extended set controls (as supportive set of controls)
- All Gant exposure mITT: Evaluated against main set controls

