16.2.3. PRIMARY ANALYSIS OF KEY SECONDARY EFFICACY VARIABLES

16.2.3.1. Primary Analysis of CDR-SB

The primary analysis will be on the All Gant Exposure mITT, with other baseline covariates (such as baseline EYO) defined in the same way as baseline for the associated population. The recurrent progression is defined as any progression which is either the first increase in CDR-SB above baseline or any progression above the highest preceding post-baseline value identified as a progression, where progression above the preceding value must be observed at two consecutive measurements unless the progression occurs at the last measurement. Subjects without a progression event at their last measurement will be censored at the time of that measurement. The time-to-event is the time elapse between the two visits where the recurrent progression is observed, or the time since the baseline assessment for the first progression. Subjects can contribute multiple records to the analysis (i.e., once for each progression and potentially for censoring at the time of last measurement). The same definition will be applied to all controls as defined in [Section 5.4](#). The Cox proportional hazards model employing the Andersen-Gill method (Prentice RL, 1981) with robust variance estimator will be used to compare the hazards of recurrent progression in CDR-SB between population and all controls. The model will include treatment group and baseline EYO as the fixed effects. Should the model produce a two-sided p-value less than 0.10, a sensitivity analysis will be conducted using the shared frailty method (add reference).

Author: [REDACTED]

Version Number:

7

Version Date:

07Dec2023

Template No.: CS_TP_BS016 Revision 6

Reference: CS_WI_BS005

Effective Date: 02Dec2019

Analyses will be conducted separately for baseline asymptomatic and symptomatic subjects.

The same analysis will be applied to the OLE Gant mITT population and the OLE Gant All Gant exposure mITT populations, along with all controls. The analysis will also be conducted for each of the three mITT populations based on the baseline asymptomatic and symptomatic subjects presented separately. A Kaplan-Meier figure will be generated for baseline asymptomatic subjects for all three mITT populations and associated controls.

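### The OLE Gant All Gant exposure mITT counts time from double-blind baseline but keeps only gantenerumab participants who later entered the OLE, so its supportive controlled comparisons can show slower progression with no drug effect

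*SAP*

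**What the plan says.** SAP 5.3 sets up three mITT populations. The second, the OLE Gant All Gant exposure mITT, is "Any subjects treated with gantenerumab in both the DB and OLE who meet mITT criteria using DB baseline as the baseline reference point".

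SAP 5.4.6 gives its comparators: "OLE Gant All Gant exposure mITT: Evaluated against main set controls (as primary set of controls) and also against extended set controls". Main set controls (5.4.3) are external DIAN-OBS controls plus internal controls, and 5.4.2 defines the internal controls as "placebo data from the double-blind period among subjects who did not enter the open-label extension". The extended set (5.4.4) adds the double-blind baseline and OLE baseline values of placebo participants who did enter the OLE.

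The population is used in these controlled analyses:
- the recurrent-progression Cox model for CDR-SB (16.2.3.1): "The same analysis will be applied to the OLE Gant mITT population and the OLE Gant All Gant exposure mITT populations, along with all controls"
- a first-progression Cox model for CDR Global (16.2.3.2)
- the LME models (16.2.3.3)
- an amyloid-subgroup analysis of CDR Global (16.2.4.2)
- the interim models (Section 17)

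SAP 3.3 calls it supportive. The primary CDR-SB and CDR Global analyses use the All Gant exposure mITT, and the primary PiB-PET analysis uses the OLE Gant mITT without controls (16.1.3).

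On OLE entry, Protocol Appendix 3, 3.2.1 requires, among other items, that the participant "is capable of receiving drug and appropriate clinical safety assessments". Appendix 3, 1.4 reports that 3 of 10 ARIA-E "cases discontinued from the trial, mainly to AD progression".

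**The concern.** Membership of the treated group is settled by something that happens after as much as 4 to 7 years of double-blind treatment (Protocol Appendix 3, 1.9.2), yet follow-up is counted from the start of those years. Gantenerumab participants who did not go on are removed, while the entrants' whole double-blind course is kept. DIAN-OBS controls face no matching rule. The internal controls face the opposite one, since they are the placebo participants who did not go on. If people who decline faster are less likely to enter the OLE, both selections favour gantenerumab.

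Nothing in the plan handles this. SAP 5.4 concedes only that control follow-up is shorter. The Cox models adjust for baseline EYO and are run by baseline symptom status. No landmark, weighting or OLE-entry adjustment is specified, and SAP 7.4 makes no multiplicity adjustment.

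At stake is the reading of the longest-exposure group. The protocol reports no benefit on the DIAN-MCE, CDR-SB or FAS in the randomised period. A hazard ratio below 1 in a selected part of that same person-time could be taken as a benefit of long treatment.

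**Working it through.** **The plan's own figure.** Protocol Appendix 3, 4.1.2: "The recruitment goal of OLE is to enroll 60 to 90 of the 144 mutation positive participants". With 5% annual dropout, 60 × 0.95³ = 51.4 and 90 × 0.95³ = 77.2, which matches the stated 51 to 77. A one-sided one-sample t-test at 0.025 with mean −0.473 and SD 0.540 has power above 99.9% at n = 51, and 81.4% at −0.22, so the stated power reproduces. It concerns PiB-PET change from OLE baseline and does not size this population.

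**Likely size of the set.** 60/144 = 41.7% and 90/144 = 62.5%. Of the 52 gantenerumab carriers (Protocol 3.3), that is 52 × 0.417 = 21.7 to 52 × 0.625 = 32.5, or about 22 to 33. This assumes equal entry across arms and that the goal was met.

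**Null simulation.**
- *From the documents:* 52 gantenerumab and 40 placebo carriers; entry fraction 41.7% or 62.5%; two-sided 5% test.
- *Assumed:* progression hazard 0.15 × exp(θU) per year, with U standard normal and θ = 0.5 or 1.0; annual visits; double-blind period 4 to 7 years, a 1-year gap and 2 years of OLE; 50, 100 or 200 external controls followed 2 to 6 years.
- *Entry:* logistic in U with log-odds −b per SD. b = 0 means entry is unrelated to progression. b = 0.5 and b = 1.0 multiply the odds of entry by exp(−0.5) = 0.61 and exp(−1) = 0.37 per SD of faster progression.
- *Drug effect:* none. Single-covariate Cox model for first progression, 1,000 trials per scenario.

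OLE entrants against main set controls, 100 external controls:

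| Selection | Median null HR | False benefit (nominal 2.5%) |
|---|---|---|
| b = 0 | 0.99 to 1.02 | 0.7% to 1.4% |
| b = 0.5 | 0.79 to 0.91 | 3.3% to 5.9% |
| b = 1.0 | 0.66 to 0.84 | 6.8% to 18.7% |

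With 50 or 200 external controls (θ = 1.0), the HR is 0.77 to 0.86 at b = 0.5 and 0.66 to 0.78 at b = 1.0. A separate null simulation against main set controls gave about 0.64 to 0.93 when entry tracked progression and about 1.0 when it did not.

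**Internal controls only** (100-external runs): 0.71 to 0.83 at b = 0.5 and 0.55 to 0.70 at b = 1.0. The opposite selection in the internal controls adds to the bias.

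**Extended controls** (100 external): 0.63 to 0.83 at b = 1.0, so they do not remove it.

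**Candidate remedies under the null with selection present.**
- All gantenerumab-randomised participants against unchanged main set controls: 0.91 to 0.98.
- The same set against external controls plus all placebo double-blind data: 0.99 to 1.00. In the simulation set out above, with gantenerumab follow-up cut at double-blind end, it was 0.97 to 1.01, with false benefit 0.9% to 2.0%.
- OLE entrants with delayed entry at OLE baseline, against main set controls: about 0.67 to 0.97. These values are noisy because few controls remain at risk by then.

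Delayed entry returns 0.995 to 1.01 only in a constant-hazard model where entry depends solely on whether progression has already occurred. When entry depends on the underlying rate of decline, entrants remain slower after OLE baseline too.

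**The case against.** The strongest reply is that the link between entry and outcome is uncertain.
- Eligibility asks for participation in the double-blind period, not completion, and states no CDR ceiling.
- Protocol 4.4.1 (item 6) keeps people who can no longer contribute key endpoints eligible for the OLE, and 6.3.6 admits any carrier for whom treatment is not contraindicated for safety and who can be dosed and assessed safely.
- Protocol 3.9 excludes those who do not want to know their mutation status. That barrier has no obvious tie to progression and might remove asymptomatic people.
- The discontinuations put down to progression are among 10 ARIA-E cases, not all gantenerumab leavers, and Appendix 3, 1.6 says ARIA-E did not raise the chance of discontinuation.

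All of this stands. It makes the size conditional but does not show that entry is unrelated to decline.

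The set is also only supportive, and the All Gant exposure mITT already covers gantenerumab in either period. Both points stand and limit the consequence. They leave the controlled comparisons for this set without a caveat on selection.

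The simulation has no EYO term, no split by symptom status and no recurrent events, so its figures illustrate size rather than predict the planned estimates. The LME bias is argued from direction only.

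A reader might infer that these models will give hazard ratios below 1 under no effect. The documents support only that they can. Nor is this strict immortal time, because CDR progression does not itself bar OLE entry.

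**Conclusion.** The concern holds as a conditional bias in a supportive population. The definition selects on later OLE entry, counts time from double-blind baseline, and compares with controls chosen without that rule or by its reverse. Under assumed moderate to strong selection the null hazard ratio is about 0.64 to 0.93; with no selection it is about 1.0. This rests on assumed hazards, entry models, follow-up and external control numbers. The documents give no count of gantenerumab leavers by reason, and the entry fraction is a recruitment goal across all arms.

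A reader might extend this to the trial's main conclusions. The documents do not support that: neither the primary PiB-PET analysis nor the primary CDR analyses use this set. One wording point needs settling, though. SAP 5.3 limits every mITT set to enrolled subjects, and 5.2 defines enrolment by OLE consent. Read literally, gantenerumab participants with double-blind data only would also leave the All Gant exposure mITT, although its definition says either period.

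**What to change.** 1. For controlled analyses timed from double-blind baseline, define the set as all participants randomised to gantenerumab who were treated and have a post-baseline assessment, whether or not they entered the OLE, with OLE data added where present.
2. Compare them with external controls plus all double-blind placebo data, not only the placebo participants who did not enter the OLE.
3. State in SAP 5.2 and 5.3 that the enrolment wording does not remove gantenerumab participants with double-blind data only.
4. If the OLE-entrant set is kept, report it as descriptive, tabulate OLE entry by progression status at the end of the double-blind period, and state the selection beside each result. Delayed entry should not be offered as the cure.

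The cost is SAP wording, a population flag, a control flag and re-runs of the affected models. No new data need to be collected. The downside is that mean gantenerumab exposure in the set falls.
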